## **2.2 STUDY TREATMENT**

Following initial standard clinical measurements for right heart catheterization, 40 ppm inhaled NO gas will be administered for approximately 5-15 minutes through a facemask, continuously monitoring subject vasoreactivity. This is considered part of the clinical right heart catheterization procedure for pulmonary hypertension. Repeat hemodynamic measurements will be performed upon completion of inhaled NO. Pre-dose baseline PK and methemoglobin levels may be collected. The inhaled nitrite will be delivered per protocol below.

Following completion of all baseline assessments, each subject will receive a starting dose of inhaled nitrite, with one subsequent planned dose escalation of inhaled nitrite, based on safety and tolerability. Subjects will be monitored carefully during and after the study treatment.

The study will be conducted at UPMC Presbyterian Hospital, 3rd FL Catheterization Laboratory. Baseline vasoreactivity will be recorded after Inhaled NO at 40 ppm for approximately 5-15 minutes. Subjects will receive a starting dose of AIR001 (45 mg), with one subsequent planned dose escalation to 90 mg based upon safety and tolerability. The dose of AIR001 will be delivered by an electronic nebulizer system that is portable, highly efficient utilizing continuously vibrating mesh aerosol generation technology that allows a high percentage respirable dose delivery, minimal loss of drug to the environment between inhalations, and a reproducible droplet size distribution for optimal delivery of drugs to the distal pulmonary tree.

During, and at approximate timelines of 15, 30, 45 and 60 minutes post-inhalation for each dose, right heart/pulmonary artery hemodynamics will be measured as well as noninvasive systemic

blood pressure monitoring. Subjects will be monitored closely during the study. Dose limiting toxicity (DLT) is defined in Table 1.

A dose level will also be considered intolerable if, in the judgment of the Investigator, the type, frequency, or severity of AEs becomes unacceptable. If an intolerable dose is identified, no further doses at that or higher doses will be administered.

**Table 1 Dose Limiting Toxicity Criteria**

Sign or Symptom	Moderate	Severe 
Bronchospasm/ wheezing	Symptomatic but not requiring therapy	Symptomatic and requiring therapy
SBP 	Systolic > 20 mm Hg drop from pre-dose baseline AND symptomatic, or SBP <80 mm Hg AND symptomatic	Systolic > 30 mm Hg drop from pre-dose baseline AND symptomatic or requiring fluid replacement or other therapy
Dyspnea	Causes more discomfort (than a mild, easily tolerated AE) and interrupts the subject's usual daily activities	Incapacitating and causes considerable interference with the subject's usual daily activities
Cough	Causes more discomfort (than a mild, easily tolerated AE) and interrupts the subject's usual daily activities	Incapacitating and causes considerable interference with the subject's usual daily activities
Hypoxia 	SaO 2 < 5% from baseline AND symptomatic	SaO 2 ≤10% baseline AND symptomatic
Venous or percutaneous methemoglobin 	>5% and <7%	≥7%
Other drug-related signs or symptoms 	Causes more discomfort (than a mild, easily tolerated AE) and interrupts the subject's usual daily activities OR CTCAE v.4  Grade 2 toxicity	Incapacitating and causes considerable interference with the subject's usual daily activities OR CTCAE v.4  Grade 3 or 4 toxicity

AE = adverse event; CTCAE = Common Toxicity Criteria for Adverse Events; DLT = dose limiting toxicity; SBP = systolic blood pressure; SaO2 = oxygen saturation (hemoglobin);

-  Severe DLT seen in any subject which is deemed to be study drug-related will preclude further dosing with AIR001 for that subject.
-  Moderate or Severe SBP without symptoms will be continuously monitored with BP measurements every 5 minutes. Symptomatic refers to dizziness or fainting. Discontinuation of further dosing will be based upon follow up blood pressure measurements, subject symptoms and physician-investigator discretion (see Stopping Rules).
-  Moderate or Severe SaO2 without symptoms will be continuously monitored and recorded every 5 minutes. As most clinically feasible; in patients with difficulty measuring SaO2 at baseline, most usually those with scleroderma but not limited to this condition, the follow up will not be based upon repeated SaO2 measurements but on clinical decision of the operating physician that will be documented as such.
-  Elevated percutaneous methemoglobin levels measured by pulse co-oximeter will be continuously monitored and confirmed by venous methemoglobin level. Follow up will be based upon the clinical decision of the operating physician and will be documented as such.
-  A single occurrence of venous methemoglobin levels >5% in an individual subject will result in no further dosing for that individual subject for the remainder of the study period
-  Common Terminology Criteria for Adverse Events v. 4.0 ([CTCAE](#)). CTCAE criteria will be applied if considered related to study drug and confirmed on repeat testing.

[figure not shown]
Baseline for the calculation of supine blood pressure changes is defined as the supine measurement taken prior to AIR001 dosing.

The presence of severe hypotension will be defined by a decrease in systolic blood pressure >30 mm Hg from pre-dose baseline AND symptomatic or requiring fluid replacement or other therapy will lead to a discontinuation of the study treatment, and the next higher dose of inhaled nitrite will not be administered to that subject. Subjects will continue to be closely monitored. Oxygen saturation will be measured by pulse oximeter and methemoglobin levels monitored by continuous co-oximetry prior to dose administration and 2 hours post last-dose will be monitored closely.

Blood samples for PK analysis, Cyclic Guanosine Monophosphate (cGMP) concentration determination, and platelet mitochondrial analysis may be collected at pre-dose and at the end of nebulization at the presumed peak nitrite concentration for each tolerated dosage time points; approximately 15 minutes post inhalation. Blood samples collected for measurements will be made on mixed venous blood using PCW pullback samples at baseline (pre-dose) and after each nitrite dose. Platelets will be isolated by differential centrifugation. Measurements of platelet mitochondrial activity will be determined at baseline (pre-dose) and after each nitrite dose.

Subjects will be monitored carefully for adverse events, laboratory test abnormalities, and changes in vital signs. Adverse experiences will be evaluated according to criteria outlined in the NCI Common Terminology Criteria for Adverse Events (CTCAE), version 4.0.

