## **2.5. SAFETY MONITORING**

Prior studies suggested that hypotension and methemoglobinemia may occur with the use of sodium nitrite. The study treatment of inhaled nitrite will be used safely with careful monitoring and prompt discontinuation of the study treatment in response to systemic hypotension with definitions of dose limiting toxicity as outlined in Table 1.

All subjects will be studied in UPMC Presbyterian Hospital Catheterization Laboratory with an investigator and nurse present at all times, and with continuous monitoring of vital signs and oxygen saturation. Subjects will also be monitored closely for methemoglobin levels during the study treatment.

Following study drug treatment, subjects will be evaluated as an outpatient at the clinic on Day 30 (+/- 5 day window). In addition, an interval telephone assessment will occur on Day 3. Subjects will be followed for evidence of acute or delayed adverse effects from the study treatment and to assess their clinical status. All adverse events experienced by subjects will be collected from the time of dosing, through the study and until the final study visit. Subjects continuing to experience toxicity at the off study visit may be contacted for additional assessments until the toxicity has resolved or is deemed irreversible. If possible, symptoms should be managed symptomatically. In the case of toxicity, appropriate medical treatment should be used.

In addition to these formal evaluations, subjects will be encouraged to immediately contact the study investigator and/or the study coordinator with questions, concerns, or to report new symptoms that occur during their study participation. If appropriate, based upon the evaluation, medical treatments will be provided to subjects, including appropriate referral to physicians or other services at the UPMC.

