## **2.6. STOPPING RULES**

In addition to the dose limiting toxicity as outlined in Table 1 above, study treatment will be discontinued if any of the following occurs:

- A decrease in systolic BP > 40 mm Hg drop from pre-dose baseline;
- Desaturation > 10% from baseline;
- A single occurrence of venous methemoglobin level >5%;
- Severe DLT criteria met and symptomatic or requiring fluids or treatment;
- Any serious adverse event thought to be possibly related to the study treatment.

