#### **\*Stopping Rule:**

For safety reasons, we propose to discontinue this study treatment if any of the following occurs:

- A decrease in systolic BP > 40 mm Hg drop from pre-dose baseline;
- Desaturation > 10% from baseline;
- A single occurrence of venous methemoglobin level >5%;
- Severe DLT criteria met and symptomatic or requiring fluids or treatment;
- Any serious adverse event thought to be possibly related to the study treatment.

The Sponsor and Investigator will prepare a detailed written summary of serious, unexpected, and treatment related adverse events, and will compare, and contrast the event with prior events. The detailed written summary will be provided to the DSMB and the IRB.

In addition, the DSMB Report addressed the following information will be submitted to the IRB at the time of continuing review annually or more often as required:

- A list of the research personnel who participated in the data and safety monitoring.
- The frequency of monitoring that took place during the renewal intervals and/or the dates that data and safety monitoring was conducted.
- A summary of cumulative data related to unanticipated problems (including adverse events) including a determination of causality and whether the risk to benefit assessment has changed.
- If appropriate, a summary of pertinent scientific literature reports, therapeutic developments, or results of related studies that may have an impact on the safety of study participants or the ethics of the research study.
- A summary of the outcome of reviews conducted to ensure subject privacy and research data confidentiality.
- Final conclusions regarding changes to the anticipated benefit-to-risk assessment of the study participation and final recommendations related to continuing, changing, or terminating the study.

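### Symptomatic systolic pressure below 80 mm Hg is graded only Moderate, and no mandatory stop before the 90 mg dose has an absolute pressure limit

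*Combined protocol and SAP*

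**What the plan says.** Each patient inhales 45 mg of nitrite and then, if safety and tolerability allow, 90 mg about an hour later. The section headed 2.2 Study Treatment states: "Dose limiting toxicity (DLT) is defined in Table 1". That table has a Moderate and a Severe column.

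- **Moderate SBP cell:** "Systolic > 20 mm Hg drop from pre-dose baseline AND symptomatic, or SBP <80 mm Hg AND symptomatic". Footnote 2 limits symptoms to dizziness or fainting.
- **Severe SBP cell:** a fall of more than 30 mm Hg from pre-dose, joined by AND to being symptomatic or needing fluids or other therapy. It has no absolute limit and no brackets. The same form appears in the synopsis, in 2.2.1 and in the text after Table 1.
- **Footnote 1:** "Severe DLT seen in any subject which is deemed to be study drug-related will preclude further dosing with AIR001 for that subject". It is silent on Moderate events.
- **Footnote 2:** stopping for SBP rests on repeat readings, symptoms and the physician's discretion, with a pointer to the stopping rules.
- **Footnote 5:** "A single occurrence of venous methemoglobin levels >5% in an individual subject will result in no further dosing for that individual subject".
- **Section 2.5:** promises "prompt discontinuation of the study treatment in response to systemic hypotension with definitions of dose limiting toxicity as outlined in Table 1", without naming a severity.
- **Section 2.6 lead-in:** "In addition to the dose limiting toxicity as outlined in Table 1 above, study treatment will be discontinued if any of the following occurs". The five bullets that follow include an SBP fall of more than 40 mm Hg and "Severe DLT criteria met and symptomatic or requiring fluids or treatment".
- **Section 5.5.2:** gives the same five bullets under a shorter lead-in, "we propose to discontinue this study treatment if any of the following occurs", with no reference to Table 1.

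**The concern.** Section 1.3.5 says the interaction of nitrite with oral therapies for pulmonary arterial hypertension is unknown. It names a clinically significant fall in systemic pressure as the worry, above all with PDE-5 inhibitors, and it relies on stopping rules that are clear. The rule that matters most is the one that decides whether a patient made hypotensive and dizzy by 45 mg goes on to twice that dose.

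As written, that decision may turn on the size of the fall alone. A patient who starts high is stopped while still at an ordinary pressure. A patient who starts low can be dizzy in the 70s and meet no mandatory numeric criterion, so the rule is loosest for those with least reserve. Effect on systemic pressure is also Specific Aim 3, and the safety hypothesis in the synopsis refers to dose-limiting symptoms, so an unsettled rule affects a study conclusion as well as patient care.

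**Working it through.** No sample size or error rate is involved. The check applies the written criteria to example patients.

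**Inputs.** Table 1 (Moderate and Severe SBP cells), the SBP bullet in 2.6 and 5.5.2 (fall above 40 mm Hg), and the entry floor in 3.3 (mean arterial pressure below 50 mm Hg is excluded). Let b be baseline SBP and s the post-dose SBP.

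**Step 1: which severity binds?** Pointing to any Table 1 toxicity: the 2.6 lead-in and 2.5. Pointing to Severe only: footnote 1 and the fourth bullet of both lists. Footnote 5 points the same way, because Moderate methemoglobin is defined as above 5% and below 7%; a separate stop for a venous level above 5% would be unnecessary if Moderate events already stopped dosing. Footnote 2 points to discretion. No sentence says outright that a Moderate SBP event must, or need not, stop dosing.

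**Step 2: the gap if only Severe binds.** Severe needs b - s > 30, so it is not met while s is at least b - 30. The absolute limit is s < 80. An untreated dizzy patient is therefore under 80 with no mandatory numeric stop when b - 30 ≤ s ≤ 79. In whole mm Hg that is 79 - (b - 30) + 1 = 110 - b values, so the gap exists for b below 110:

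- b = 109: s = 79 (1 value)
- b = 105: s = 75 to 79 (5)
- b = 100: s = 70 to 79 (10)
- b = 90: s = 60 to 79 (20)

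**Step 3: worked patients, all untreated.**

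| b to s | Dizzy | Fall | Moderate | Severe | Fall > 40 |
|---|---|---|---|---|---|
| 105 to 77 | yes | 28 | yes | no | no |
| 90 to 75 | yes | 15 | yes | no | no |
| 109 to 79 | yes | 30 | yes | no | no |
| 110 to 79 | yes | 31 | yes | yes | no |
| 145 to 114 | yes | 31 | yes | yes | no |
| 160 to 119 | no | 41 | no | no | yes |

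The last three are stopped on any reading (a Severe event, if judged drug-related under footnote 1). The first three are stopped only if Moderate events bind.

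**Step 4: does entry close the gap?** Assuming mean pressure = (SBP + 2 × DBP)/3, a floor of 50 requires DBP ≥ (150 - SBP)/2. That is 22.5 at SBP 105, 25 at SBP 100 and 30 at SBP 90. The floor does not keep these patients out.

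**Step 5: the unbracketed Severe criterion.** Reading A is fall > 30 AND (symptoms OR therapy). Reading B is (fall > 30 AND symptoms) OR therapy. They differ only when therapy is given and the fall is 30 mm Hg or less. A patient going from 95 to 75, dizzy and given fluids (fall 20), is Moderate under A and Severe under B. One going from 120 to 95, without symptoms but given fluids (fall 25), is ungraded under A and Severe under B. Under A, the gap in Step 2 also covers treated patients.

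**The case against.** The best defence is that the text can be read coherently. Drug-related Severe toxicity is a mandatory stop, and footnote 2 deliberately leaves other SBP events to the physician. The 2.6 lead-in refers to toxicity as Table 1 sets it out, which can include those footnotes. A reader might infer a flat contradiction between sections, but the documents do not support that: section 2.2 only defines toxicity, and the rest is compatible with discretion. Nor does the shorter lead-in in 5.5.2 permit re-dosing; protocol rules accumulate, and silence in one list does not cancel another.

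The safeguards are also real. The 90 mg dose is conditional on safety and tolerability, and the investigator may call a dose intolerable (2.2). An investigator and nurse are present throughout with continuous vital signs (2.5). Fluids and vasopressors are at hand (1.3.5). Oral endothelin antagonists and PDE-5 inhibitors are held that day. Section 5.1 withholds the next dose after a significant pressure drop, though it gives no threshold. The 90 mg dose is below the 125 mg maximum tolerated dose, at which systolic pressure changed by -3 +/- 2 mm Hg, though in normal volunteers. A possibly related serious adverse event, or a Severe event in the table's row for other drug-related signs, would also stop dosing.

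Two narrower points stand. For b of 100 or more, any s below 80 is a fall above 20, so the first Moderate limb already applies; the below-80 limb changes the grade only for b under 100. And reading A is the more natural one: the Moderate cell marks its second limb with a comma, and the Severe cell has none.

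This narrows the point without removing it. The safeguards rest on judgement, and none supplies a mandatory absolute limit.

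**Conclusion.** The point holds as a cheap safety improvement. No mandatory Severe or stopping-list criterion contains an absolute SBP limit, and the text leaves open whether a Moderate SBP event bars 90 mg. If only Severe toxicity binds, the uncovered range is b - 30 to 79 mm Hg for untreated dizzy patients with baseline below 110, and it widens as baseline falls.

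A reader might go further and infer that the protocol leaves such patients unprotected or allows re-dosing. It does not: discretion applies throughout, and what is missing is a mandatory rule. How many patients are affected cannot be estimated, because no baseline SBP distribution is given. The result assumes the Severe-only reading and, for the entry check alone, the usual mean-pressure formula. CTCAE thresholds, which could bring some events under the table's row for other signs, are not in the documents.

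**What to change.** 1. Add to the lists in both 2.6 and 5.5.2: *SBP below 80 mm Hg with dizziness or fainting, whatever the size of the fall*. Moving that criterion to the Severe column of Table 1 would serve equally well.
2. Give both lists the same lead-in, and state in it whether other Moderate SBP events (a symptomatic fall above 20 mm Hg that does not go below 80) bar 90 mg or remain at the physician's discretion.
3. Bracket the Severe SBP criterion identically in the synopsis, 2.2.1, Table 1 and the text after Table 1, and bracket the fourth bullet of both lists to match. The natural form is: fall above 30 mm Hg AND (symptomatic OR requiring therapy). Making treated hypotension a stop whatever the fall may be sensible, but it would be a deliberate safety change and should be presented as one, not as a clarification.

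The cost is an amendment to wording, with no new measurement or visit. The downside is that a few patients may not receive 90 mg, mainly patients whom a careful investigator would probably have stopped anyway.

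### The Table 1 hypoxia row does not state a usable dosing threshold, and none of its plausible readings agrees with the stopping rules

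*Combined protocol and SAP*

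**What the plan says.** The Study Treatment section (the second section numbered 2.2) makes Table 1 the definition of dose limiting toxicity. The passages that bear on hypoxia are these.

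- **Table 1, Hypoxia, Moderate:** SaO2 "< 5% from baseline AND symptomatic".
- **Table 1, Hypoxia, Severe:** SaO2 "≤10% baseline AND symptomatic".
- **Table 1, SBP, Severe, for comparison:** "Systolic > 30 mm Hg drop from pre-dose baseline AND symptomatic or requiring fluid replacement or other therapy". The Moderate SBP cell has the same form with a limit of 20 mm Hg.
- **Footnote 1:** "Severe DLT seen in any subject which is deemed to be study drug-related will preclude further dosing with AIR001 for that subject".
- **Footnote 3:** Moderate or Severe SaO2 changes "without symptoms will be continuously monitored and recorded every 5 minutes".
- **Section 2.6, opening:** "In addition to the dose limiting toxicity as outlined in Table 1 above, study treatment will be discontinued if any of the following occurs". The list includes "Desaturation > 10% from baseline", with no symptom condition. Its fourth bullet stops treatment when Severe DLT criteria are met together with symptoms or a need for fluids or treatment.
- **Section 5.5.2:** repeats the same stopping list.

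**The concern.** A threshold that governs dosing has to tell the operator which way saturation must move, by how much, and in what units. The SBP row does this: it names a drop, and its limit rises from Moderate to Severe. The hypoxia row names no drop, and its inequality signs are opposite to the one in the desaturation stopping rule.

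The row matters because Severe DLT gates dosing twice. Footnote 1 bars further AIR001 after a drug-related Severe DLT. The fourth stopping bullet also depends on the Severe criteria and does not mention drug-relatedness. The row therefore helps decide who goes on from 45 mg to 90 mg.

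That carries through to efficacy. Section 2.15.2 compares baseline with the highest tolerated nitrite dose, and the final measurements in Section 2.10.2 follow the last tolerated dose.

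**Working it through.** No sample size, power or alpha figure is involved. The check sets the printed cells against the stopping rule for a range of falls.

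**Inputs.** The two hypoxia cells and footnotes 1 and 3 of Table 1, and the desaturation bullet of Sections 2.6 and 5.5.2. Let *f* be the fall in SaO2 from baseline, in percent, in a symptomatic subject.

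**Reading A, the cells as the size of a fall.** Moderate if *f* < 5; Severe if *f* ≤ 10.

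**Reading B, the cells as saturation below baseline by those amounts.** Moderate if *f* > 5; Severe if *f* ≥ 10.

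**Desaturation bullet.** Stop if *f* > 10.

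| Fall (%) | A: Moderate | A: Severe | B: Moderate | B: Severe | Desaturation bullet |
|---|---|---|---|---|---|
| 1 | yes | yes | no | no | no |
| 3 | yes | yes | no | no | no |
| 5 | no | yes | no | no | no |
| 7 | no | yes | yes | no | no |
| 10 | no | yes | yes | yes | no |
| 10.1 | no | no | yes | yes | yes |
| 12 | no | no | yes | yes | yes |
| 20 | no | no | yes | yes | yes |

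**Under A**, Moderate (below 5) lies wholly inside Severe (up to 10). Severe and the stopping range (above 10) are exact complements. A 1% fall with symptoms is Severe; a 12% fall has no hypoxia grade.

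**Under B**, the grades rise in order, but three problems remain.

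1. A fall of exactly 10% is Severe but does not exceed 10%, so the two definitions part at the boundary. The fourth stopping bullet would still stop a symptomatic subject there, so this is mainly a mismatch of definitions.
2. Take a 12% fall without symptoms. Footnote 3 calls for monitoring and recording. The desaturation bullet calls for discontinuation. Footnote 2, on blood pressure, refers the reader to the stopping rules; footnote 3 does not. Footnote 3 also speaks of graded SaO2 changes without symptoms, although both cells require symptoms.
3. Moderate has no upper bound, so falls of 10% or more meet both grades unless the higher is understood to apply. The methemoglobin row avoids this by giving Moderate an upper bound.

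**Reading C, the Severe cell as 10% of the baseline value.** At an assumed baseline of 95%, 0.10 × 95 = 9.5, an SaO2 of 9.5% or lower. That is not a workable limit.

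**Units.** A relative fall of 10% equals 0.10 × baseline, in points. Baselines below are assumed.

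| Baseline SaO2 | Relative 10% (points) | Absolute 10 (points) | Difference |
|---|---|---|---|
| 85 | 8.5 | 10 | 1.5 |
| 90 | 9.0 | 10 | 1.0 |
| 95 | 9.5 | 10 | 0.5 |

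So from a baseline of 85%, a 9-point fall is 9/85 = 10.6% in relative terms and meets the desaturation bullet, but does not meet it in absolute points.

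**Undefined terms.** The Study Treatment section defines baseline only for blood pressure, and footnote 2 explains symptomatic only for SBP.

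**The case against.** The best defence is that the cells speak of SaO2 itself, not of a fall. On that footing a less-than sign naturally means saturation lower than baseline, much as the SBP row uses one for a systolic pressure under 80 mm Hg. Reading B is then the intended one and the grades are in order. This stands in part: a reader might infer that the limits simply run the wrong way, but that depends on Reading A. Both readings supply words that are not printed. The supported conclusion is that the row is undetermined, and Reading B still conflicts with the stopping rules.

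A reader might also infer that subjects with large falls could stay on drug because they meet neither grade. The documents do not support this. The stopping rules are additive, so any fall above 10% stops treatment whatever Table 1 says. Symptomatic falls might also be graded under the dyspnea row or the row for other drug-related signs. The investigator may declare a dose intolerable, and saturation is monitored continuously with an investigator and a nurse present.

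Nor is a planned DLT analysis distorted. The safety analysis in Section 2.15.2 lists adverse event summaries and no DLT count. Escalation is within each subject, and no rule sets a later dose from a number of DLTs.

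Finally, a subject stopped after 45 mg still contributes to the primary comparison through the highest tolerated dose. That is correct, but the dose contributed would then have been decided by an unclear rule.

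A symbol lost in converting the document cannot be fully excluded. Against it, both hypoxia cells point the same way, and the methemoglobin row prints its signs in correct order. The sponsor can check the source file.

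**Conclusion.** The hypoxia row does not state a usable dosing threshold. Reading A makes Severe the complement of the stopping range. Reading B orders the grades but leaves the boundary mismatch at 10%, the conflict with footnote 3 and the undefined units. Reading C is unworkable.

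The effect is limited to misclassified hypoxia DLTs and needless or inconsistent withholding of the second dose, and through that to which dose enters the primary comparison for the affected subjects. Under Reading A, any symptomatic fall of up to 10% could end dosing. The number of subjects affected cannot be estimated, because the documents give no expected rate of symptomatic desaturation.

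The conclusion assumes that the inequality signs are as printed. The units comparison also assumes baselines of 85% to 95%. The defect merits correction because it sits in a rule that gates dosing, not because the documents leave large falls unmanaged.

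**What to change.** Reconcile four places: the two hypoxia cells of Table 1, footnote 3, and the desaturation bullets of Sections 2.6 and 5.5.2. Write each grade as an explicit fall from pre-dose SaO2. State the direction, the units (absolute points or relative percent) and whether symptoms are required, and make the bands non-overlapping. Use consistent wording in all four places, and say how a symptom-free fall within the stopping range is handled, so that footnote 3 and the stopping rules agree. The sponsor must set the limits and the handling; none is proposed here.

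The cost is a wording amendment to one table row, one footnote and two repeated bullets, with IRB approval of the modification under Section 6.3. No procedures, visits or subjects are added.
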